7.8 Investigator Assessments

The investigator assessments are to be performed by a dermatologist or a physician with at least 1 year of experience in dermatology. For physicians who do not fulfill the requirement regarding dermatological experience, the person must be preapproved by the sponsor. Preferably the same investigator will assess the subject throughout the trial. The assessments are to be performed as specified in the visit schedule Table 7-1.

7.8.1 Body surface area (BSA) involvement of psoriasis vulgaris on the body

The total psoriatic involvement on the body and scalp will be recorded as a percentage of the total BSA, estimating that the surface of the subject's full, flat palm (including the five digits) correlates to approximately 1% of the total BSA.

The investigator will assess:

- the extent of the subject's psoriatic involvement on the body (excluding scalp, face, genitals, and intertriginous areas).
- the extent of the subject's psoriatic involvement on the scalp.

7.8.2 Modified Psoriasis Area and Severity Index (mPASI)

At all on site visits, the investigator will assess the extent and severity of the subjects' psoriasis on the body (trunk and/or limbs) (i.e. the scalp is not involved in this assessment) using an mPASI scoring system.

The extent of psoriatic involvement (extent (E)) will be recorded for each of the 3 areas (arms, trunk, and legs) using the following scale:

0 = no involvement	
1 = < 10%	4 = 50% - 69%
2 = 10% - 29%	5 = 70% - 89%
3 = 30% - 49%	6 = 90% - 100%

The severity of the psoriatic lesions in each of the 3 areas will be recorded for each of the signs of redness, thickness, and scaliness. For each clinical sign, a single score, reflecting the average severity of all psoriatic lesions on given body region, will be determined according to the scale below:

Redness

0	=	none (no erythema)
1	=	mild (faint erythema, pink to very light red)
2	=	moderate (definite light red erythema)
3	=	severe (dark red erythema)
4	=	very severe (very dark red erythema)

Thickness

0	=	none (no plaque elevation)
1	=	mild (slight, barely perceptible elevation)
2	=	moderate (definite elevation but not thick)
3	=	severe (definite elevation, thick plaque with sharp edge)
4	=	very severe (very thick plaque with sharp edge)

Scaliness

0	=	none (no scaling)
1	=	mild (sparse, fine-scale lesions, only partially covered)
2	=	moderate (coarser scales, most of lesions covered)
3	=	severe (entire lesion covered with coarse scales)
4	=	very severe (very thick coarse scales, possibly fissured)

The m-PASI is calculated from the scores given by the (sub)investigator during their assessment of the extent and severity of the disease by use of the following equation:

Arms 0.2 (R + T + S) E = XTrunk 0.3 (R + T + S) E = Y

Legs 0.4 (R + T + S) E = Z

Where: R =score for redness; T =score for thickness; S =score for scaliness; E =score for extent.

The sum of X + Y + Z equals the m-PASI score resulting in a minimum score of 0 and a maximum score of 64.8.

MC2 Therapeutics

Confidential

7.8.3 Physician's global assessment of psoriasis severity

The Physician's Global Assessment (PGA) measures the investigator's impression of the disease at a single point using a defined, 5-point, static PGA scale (clear, almost clear, mild, moderate or severe); see Table 7-3.

The PGA assessment should be made separately for the body (trunk and/or limbs) and the scalp.

The PGA assessment will represent the *average* lesion severity on the two body locations. The assessments will be based on the condition of the disease at the time of evaluation, and not in relation to the condition at a previous visit.

Score	Grade	Definition		
0	Clear	Plaque thickening = no elevation or thickening of normal skin		
		Scaling = no evidence of scaling		
		Erythema = none (no residual red colouration but post-inflammatory		
		hypo or hyperpigmentation may be present)		
1	Almost	Plaque thickening = none or possible thickening but difficult to ascertain		
	clear	whether there is a slight elevation above normal skin level		
		Scaling = none or residual surface dryness and scaling		
		Erythema = light pink colouration		
2	Mild	Plaque thickening = slight but definite elevation		
		Scaling = fine thin scales partially or mostly covering lesions		
		Erythema = light red colouration		
3	Moderate	Plaque thickening = moderate elevation with rounded or sloped edges		
		Scaling = coarse scale layer at least partially covering most lesions		
		Erythema = definite red colouration		
4	Severe	Plaque thickening = marked or very marked elevation typically with hard or sharp edges		
		Scaling = non-tenacious or thick tenacious scale predominates, covering most or all of the		
		lesions		
		Erythema = very bright red colouration, extreme red coloration or deep red coloration		

 Table 7-3 Physician's Global Assessment (PGA)

7.8.4 Local skin reactions

The local skin reaction assessment involves signs assessed by the investigator.

MC2 Therapeutics

The investigator will assess the treatment area and/or immediate surrounding for the following identified signs:

- Perilesional erythema, scaling, edema, atrophy, vesicles and erosion/ulceration;
- Lesional vesicles, and erosion/ulceration.

The intensity of each local skin reaction category is to be graded according to the scale in Table 7-4. The most severe intensity observed for each category of the local skin reaction assessment is to be recorded.

Table 7-4 Local Skin Reaction Scores

Investigator assessment of the lesional area						
	0 (absent)	1 (Mild)	2 (Moderate)	3 (Severe)		
Erosion/ulceration in lesional area	None	Barely visible erosion	Distinct erosion	Ulceration		
Vesicles in lesional area	None	Barely visible vesicles	Distinct vesicles	Bullae		
Investigator assessment	of the perilesional	area	1	1		
	0=absent	1 (Mild)	2 (Moderate)	3 (Severe)		
Erythema in perilesional area	None	Barely visible erythema	Distinct erythema	Dark red erythema		
Scaling in the perilesional area	None	Barely visible scaling	Distinct scaling	Gross scales		
Edema in perilesional area	None	barely palpable swelling	Easily palpable swelling	Gross swelling		
Atrophy in perilesional area	None	Barely visible thinning	Distinct thinning	Striae		
Vesicles in perilesional area	None	Barely visible vesicles	Distinct vesicles	Bullae		
Erosion/ulceration in perilesional area	None	Barely visible erosion	Distinct erosion	Ulceration		

7.9 Patient Reported Outcomes (PROs)

The PRO instruments must be completed by the subjects before any other assessments are performed. The PRO assessments are to be performed as specified in the visit schedule (Table 7-1).

7.9.1 Subject Global Assessment of disease severity (SGA)

Subjects will grade the overall severity of their symptoms according to the following 5-point scale:

- 0 =Clear; no psoriasis symptoms at all.
- 1 = Very mild; very slight psoriasis symptoms that do not interfere with daily life.
- 2 = Mild; slight psoriasis symptoms that interfere with daily life only occasionally.
- 3 = Moderate; definite psoriasis symptoms that interfere with daily life frequently.
- 4 = Severe; intense psoriasis symptoms that interfere or restrict daily life very frequently.

7.9.2 Dermatology Life Quality Index (DLQI)

The DLQI(26) is a validated questionnaire consisting of 10 questions relating to the degree to which the subject's skin condition affected their daily activities.

7.9.3 EuroQOL five dimensions questionnaire (EQ-5D)

The EQ-5D is one of the most commonly used generic questionnaires to measure health-related quality of life (QOL)(27). It consists of a questionnaire and a visual analog scale (EQ-VAS). The EQ-VAS records the subject's perceptions of their own current overall health and can be used to monitor changes over time. The self-assessment questionnaire is a self-reported description of the subject's current health in 5 dimensions i.e., mobility, self-care, usual activities, pain/discomfort, and anxiety/depression.

7.9.4 The Psoriasis Treatment Convenience Scale

The Psoriasis Treatment Convenience Scale must be completed by the subjects before any other assessments are performed. The assessments are to be performed as specified in the visit schedule (see Table 7-1).

The aim of the Psoriasis Treatment Convenience Scale is to assess the impact and convenience of psoriasis treatment. The scale has been tested for content validity through focus group interview with 20 patients and adapted based on the responses. The scale consists of 6 disease-specific, self-report questions with a recall period of 1 week and rated on a 1-10 point scale.

- 1. How easy was the treatment to apply to the skin?
- 2. How greasy was the treatment when applying it to the skin?
- 3. How moisturised did your skin feel after applying the treatment?
- 4. How greasy did your skin feel after applying the treatment?

- 5. How much did treating your skin disrupt your daily routine?
- 6. Overall, how satisfied were you with the medical treatment?

7.9.5 Photography

Colour photographs of the treatment area should be taken as specified in the visit schedule (see Table 7-1).

MC2 may at its discretion use the photographs in publication or similar types of information material for health care professionals. The photographs can also be part of the training material used for training and educational purposes. Use of photographs for these purposes is optional and requires prior consent by the subject.

MC2 will ensure that all necessary steps to ensure the anonymity of the subject are taken (e.g. masking of face, no photos of characteristic details on the body, etc.

7.10 Adverse Events

7.10.1 Adverse events assessments

The investigator is responsible for obtaining, assessing, and documenting all AEs during the trial. Adverse Events information will be collected from the time of the signature of the informed consent form and first trial-related activity performed until the end of the trial. An AE is an untoward medical occurrence in any subject during the trial which does not necessarily have a causal relationship with the IP.

All AEs will be documented in the eCRF, including a description of each AE, AE relationship to IP administration, start and stop dates, seriousness, severity, action taken and outcome.

Any AE that meet the serious criteria must be reported on the eCRF and on a separate SAEs report form. SAEs must be reported immediately to MC2 or designee as soon as it becomes known to the investigator and not later than within 24 hours of his/her knowledge of the occurrence of an SAE.

Throughout the trial, the occurrence of AEs should be sought by nondirective questioning of the subject at each visit during the trial. Information on AEs can also be obtained from signs and symptoms detected during examination, observations made by the trial site personnel, or spontaneous reports from subjects. Pre-existing conditions that worsen during the trial should also be recorded as AEs. This will also include worsening of the psoriasis vulgaris as judged by the investigator.

AEs requiring therapy must be treated with recognised standards of medical care to protect the health and well-being of the subject. Treatment due to an AE will be recorded in the subject's records and on the appropriate eCRF.

Any AE that is considered related to the IP must be followed by the investigator until it is resolved or until the medical condition of the subject is stable; all relevant follow-up information will be reported to MC2 or designee.

The outcome of an AE will be classified as recovered, recovered with sequelae, recovering/resolving, ongoing, or death.

7.10.2 Timing

AEs will be collected during the period from the time of the signature of the informed consent form and first trial-related activity performed until the end of the trial.

7.10.3 Severity of adverse events

The investigator is to classify the severity (intensity) of an AE according to the following definitions:

- Mild The subject was aware of the signs and symptoms, but the signs and symptoms were easily tolerated and do not interfere with daily activity.
- Moderate The signs and symptoms were sufficient to restrict, but did not prevent, usual daily activity for the subject. The subject is still able to function.
- Severe The subject was unable to perform usual daily activity.

The maximum intensity of an AE (mild, moderate, or severe) will be assessed taking into account the possible range of intensity of the symptom(s).

7.10.4 Relationship of an adverse event to trial treatment

The investigator is responsible to assess the relationship of an AE to the IP treatment using good clinical judgment and the following definitions:

Not Related	The AE is clearly explained by another cause not related to the IP administration; the temporal relationship of the AE to IP administration makes a causal relationship unlikely, or, concomitant medication, therapeutics interventions, or underlying condition provide a sufficient explanation for the observed AE
Possibly Related	The AE and administration of IP are temporally related, but the AE can be explained equally well by causes other than the IP administration
Probably Related	The AE and use of IP are temporally related, and the AE is more likely explained by IP administration than by other causes

MC2-01-C7

16 October 2018 Version 2.0

Definitely Related The AE and IP administration are related in time, and a direct association can be demonstrated. Concomitant medication, therapeutics interventions, or underlying conditions do not provide a sufficient explanation for the observed AE

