2.3 Benefit-risk Assessment

The subject population will be composed of subjects with mild to moderate psoriasis; their psoriasis is expected to be manageable with topical therapy.

The active ingredients in the investigational products (CAL and BDP) are known to be effective for the treatment of psoriasis. The safety and efficacy profiles for marketed products with these ingredients (formulated as ointment, gel/topical suspension and more recently aerosol foam) are well known. A cream formulation of CAL and BDP may benefit subjects by providing improved convenience and ease of use resulting in increased patient adherence to therapy which will improve real-life treatment outcome (22).

According to the SmPC for Daivobet gel, the common AE (>1%) is pruritus. Uncommon (i.e. $\geq 0.1\%$ and < 1%) AEs are folliculitis, skin infections, exacerbation of psoriasis, dermatitis, erythema, rash, skin irritation, skin burning sensation, application site pain, as well as eye irritation (probably related to use on scalp).

The available data on MC2-01 cream suggest that MC2-01 cream will display a similar safety profile as the approved CAL/BDP topical products. A Phase 3 trial with MC2-01 cream and a maximal usage trial in adults have completed enrolment. As of the cut-off date of this clinical trial

MC2 Therapeutics

protocol, the adverse event reported is as expected and no serious unexpected serious adverse reactions (SUSARs) have been reported.

A subset of subjects will receive a cream vehicle. There is a risk that psoriasis symptoms may worsen in these vehicle-treated subjects; while an exacerbation of psoriasis may be inconvenient, it would not put the subjects at undue risk. In case of inadequate efficacy, the subject can decide to withdraw and then receive alternative therapy according to her/his choice.

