7.10.5 Unexpected adverse events

Any AE assessed at least as possibly related to the IP will be assessed for expectedness by the sponsor or designee. An AE is considered "unexpected" if its nature or severity is not consistent with information in the MC2-01 Investigator's Brochure(23) (for MC2-01 cream) or Daivobet[®] / Dovobet[®]Gel Summary of Product Characteristics (SmPC)(24) (for active comparator).

"Unexpected" as used in this definition, also refers to AEs that are mentioned in the Investigator's Brochure or SmPC as occurring with a class of drugs or as anticipated from the pharmacological properties of the drug but are not specifically mentioned as occurring with the particular drug under investigation.

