2.4.2 Safety and Tolerability

Local Skin Reaction

Assessments of local skin reaction (LSR) will be performed by the investigator at all on-site post-screening visits. The treatment area and/or immediate surrounding for the following identified signs will be assessed:

- Perilesional erythema, scaling, edema, atrophy, vesicles and erosion/ulceration;
- Lesional vesicles, and erosion/ulceration.

The intensity of each local skin reaction category is to be graded according to the scale in the following table. The most severe intensity observed for each category of the local skin reaction assessment is recorded.

Category		Intensity			
Area	Sign	0 = absent	1 = mild	2 = moderate	3 = severe
Lesional	Erosion/ ulceration	none	barely visible erosion	distinct erosion	Ulceration
	Vesicles	none	barely visible vesicles	distinct vesicles	Bullae
Perilesional	Erythema	none	barely visible erythema	distinct erythema	dark red erythema
	Scaling	none	barely visible scaling	distinct scaling	gross scales
	Edema	none	barely visible swelling	easily palpable swelling	gross swelling
	Atrophy	none	barely visible thinning	distinct thinning	Striae
	Vesicles	none	barely visible vesicles	distinct vesicles	Bullae
	Erosion/	none	barely visible erosion	distinct erosion	Ulceration
	ulceration		-		

Table 2: Overview of intensity grading of local skin reaction by area and sign

An LSR sum score is defined as the sum of intensity grades across all areas and signs per visit. Per sign, the most intense reaction is defined as the maximum intensity grade across visits.

Adverse Events

All adverse events (AE) are recorded with the following attributes:

- severity (mild, moderate, severe),
- location of AE to treatment area,
- action taken (none, concomitant therapy, concomitant non-drug therapy),
- action taken with IP (dose not changed, dose reduced, dose increased, dose interrupted, drug withdrawn, not applicable, unknown, other)
- outcome (recovered, resolved with sequelae, recovering/ resolving, ongoing, death),
- withdrawal due to AE,
- start and end dates,
- relationship to IP (definitely related, probably related, possibly related, not related),
- relationship to study procedure,
- seriousness, criterion for seriousness (death, life-threatening, hospitalization, disability/incapacity, congenital anomaly/birth defect, other).

Any AE is treatment-emergent, if fulfilling the definition in Section 4.4.5.

Any AE is a drug-related AE, if relationship to IP is not assessed as *not related*.

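### Causality categories in Protocol 7.10.4 are not mutually exclusive: an AE that psoriasis explains sufficiently, and about as well as the product does, is both Not Related and Possibly Related

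*Protocol*

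**What the plan says.** Protocol 7.10.4 gives the investigator four classes and asks for clinical judgement in applying them.

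- **Not Related** can be reached by any of three routes joined by an 'or': another cause clearly accounts for the AE; the timing makes a causal link improbable; or "concomitant medication, therapeutics interventions, or underlying condition provide a sufficient explanation for the observed AE".
- **Possibly Related** applies when the AE and the product are "temporally related, but the AE can be explained equally well by causes other than the IP administration".
- **Probably Related** applies when the timing fits and the product is the likelier explanation.
- **Definitely Related** requires, among other things, that concomitant treatment and "underlying conditions do not provide a sufficient explanation for the observed AE".

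The split between Not Related and the other three classes is then used in several places. SAP 2.4.2 states: "Any AE is a drug-related AE, if relationship to IP is not assessed as" not related. Protocol 7.10.5 states: "Any AE assessed at least as possibly related to the IP will be assessed for expectedness". Protocol 7.10.1 requires AEs considered related to be followed until they resolve or the subject is stable. Of pre-existing conditions that worsen and must be recorded as AEs, the same section says: "This will also include worsening of the psoriasis vulgaris as judged by the investigator".

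**The concern.** A causality scale should place each event in one class. Here the third route to Not Related asks only whether the underlying condition is a sufficient explanation. It does not ask whether the product is a less likely one. Two investigators can therefore follow the text correctly and file the same event on opposite sides of the only boundary the SAP uses to define drug-related.

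The trial's secondary objective is the safety profile of MC2-01 cream, assessed at about 34 sites. The disease lies on the skin being treated, so the affected type of event is a realistic one. Protocol 2.3 says of the comparator gel that "the common AE (>1%) is pruritus", and its list of uncommon reactions includes exacerbation of psoriasis, erythema and skin irritation. Psoriasis could plausibly account for several of these.

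**Working it through.** No arithmetic applies. Neither document states a rate or count at this boundary, so the check sets the definitions side by side and traces where the result is used.

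**Step 1: do the two definitions share cases?** Take an AE on treated skin during daily application. The timing fits, so the second route to Not Related is closed and the first condition of Possibly Related is met. Suppose the product would account for the AE, and psoriasis accounts for it equally well. The second condition of Possibly Related is then met. If psoriasis explains the event as well as an adequate explanation does, psoriasis is itself a sufficient explanation, so the third route to Not Related is also met. The event is in both classes.

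**Step 2: does other wording in the section prevent this?** Definitely Related is the only related class that excludes a sufficient alternative explanation. Possibly Related and Probably Related carry no such exclusion. The section has no order of precedence and no tie-break beyond clinical judgement.

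**Step 3: what follows from the choice?**

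| Use of the split | If Possibly Related | If Not Related |
|---|---|---|
| Tables 14.3.1.4 and 14.3.1.5 (drug-related AEs; by maximum severity) | in | out |
| Table 14.3.1.7 (drug-related SAEs), if serious | in | out |
| Table 14.3.1.9 (drug-related AEs in the treatment area) | in | out |
| Expectedness review, Protocol 7.10.5 | done | not required |
| Required follow-up to resolution or stability, Protocol 7.10.1, non-serious AEs | required | not required |
| Tables 14.3.1.2 and 14.3.1.3 (all treatment-emergent AEs) | in | in |
| SAE reporting and SAE follow-up reports, Protocol 7.10.8 and 7.10.9.2 | required | required |

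Table 14.3.1.9 is the only treatment-area table in the SAP's Table 6. Location relative to the treatment area is recorded for every AE (SAP 2.4.2), yet a treatment-area AE filed as Not Related appears in no table by location.

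**Step 4: the on-site follow-up visit.** Protocol 7.12 ties this visit to unresolved AEs that are treatment-related, or to raised albumin-corrected calcium. SAP 2.1 ties it to abnormal laboratory values or unresolved AEs, with no relatedness condition. Whether the causality call affects this visit depends on which document is followed.

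**The case against.** The strongest reply is that a sensible investigator would read the third route beside the first, which needs a clear alternative cause, and would leave ties to Possibly Related, whose text already speaks of equal explanations. That reading is coherent, but the text does not require it. The routes are alternatives, and the third adds something to the first only if it sets a different test.

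Three stronger readings are tempting, and the documents do not support them.

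- **That every treatment-area AE psoriasis could explain is in the overlap.** The text requires a sufficient explanation, not a conceivable one. An AE that psoriasis explains only weakly fails that test. One that the product explains better is described by Probably Related. The firm overlap is limited to AEs that psoriasis explains sufficiently and about as well as the product.
- **That such AEs disappear from reporting.** They stay in the all-causality tables and the listings. Perilesional erythema, scaling, edema and atrophy, and vesicles and erosion in either area, are also graded as local skin reactions with no causality judgement (Protocol 7.8.4). That scale does not cover pruritus or burning, and it grades erythema only around the lesion, so it replaces AE classification only in part.
- **That the distortion can be given a size or a direction.** The documents give no rate for these events, so any percentage would be invented. Assessors are blinded to treatment, and the wording alone gives no reason to expect bias between arms.

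The expectedness point also has limits. Pruritus, erythema, irritation and exacerbation of psoriasis are taken from the comparator's product information, so for that product only greater severity could make them unexpected. For MC2-01 cream the reference is the Investigator's Brochure, which is not among the documents. All SAEs reach the sponsor whatever the causality call, although SUSAR status still depends on it.

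**Conclusion.** The overlap is real and follows from the wording of Protocol 7.10.4. It is a conflict between two stated rules, not a missing detail. For AEs in the overlap, the drug-related count in an arm could be anything from none of them to all of them under correct use of the same text. How many there will be cannot be estimated from the documents.

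The effect is confined to the four drug-related tables, the expectedness review, and required follow-up of non-serious AEs. Efficacy results, power and SAE reporting are unaffected, and the safety analyses are descriptive. The correction is worth making because it is small and the affected tables bear on the secondary objective. The conclusion assumes that no tie-break exists elsewhere. An eCRF completion guide might contain one, but none is among the documents.

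**What to change.** 1. In Protocol 7.10.4, reword the third route to Not Related so that the concomitant medication, intervention or underlying condition must be a more likely explanation than the product. Equal plausibility then falls to Possibly Related alone. Carry the same wording into any eCRF guidance.
2. In the SAP's Table 6, add a table of treatment-emergent AEs located in the treatment area regardless of causality, beside Table 14.3.1.9. The location data are already collected, and this table does not depend on how the boundary was applied.
3. Reconcile SAP 2.1 with Protocol 7.12 on when the follow-up visit is held on site.

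The first change is not administrative, so under Protocol 9.1 it needs a written amendment and ethics approval. Events classified before it takes effect would have been judged under the present wording, which is a further reason for the second change. The reported drug-related AE rate may come out slightly higher. The SAP change costs one table.
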